Ethnic Differences in Antihypertensive Medication Response among Pregnant and Postpartum Patients

[name]

NCT03506724

11/2017

Protocol

Patients were randomized to first receive IV labetalol or oral nifedipine and the number of doses of each medication that was given was recorded. The protocol used for medication administration was the same as the ACOG protocol for treatment of acute hypertension in pregnancy (See medication specific protocol below). Blood pressure for all women in the study was taken in the right arm with an automated blood pressure cuff while the patient was resting in bed in the semi-recumbent position. The systolic blood pressure and diastolic blood pressure was recorded before and after administration of each medication. A short survey to assess patient-reported side effects were provided prior to and post medication administration.

IV Labetalol protocol

Labetalol 20mg IV was given over 2 minutes and the systolic and diastolic blood pressures were recorded 10 minutes after the medication was given. If SBP was ≥ 160 mmHg or DBP was ≥ 110 mmHg, labetalol 40mg IV was given over 2 minutes and the systolic and diastolic blood pressures were recorded 10 minutes after the medication was given. If SBP was ≥ 160 mmHg or DBP was ≥ 110 mmHg, labetalol 80mg IV was given over 2 minutes and the systolic and diastolic blood pressures were recorded 10 minutes after the medication was given. If SBP was ≥ 160 mmHg or DBP was ≥ 110 mmHg, then another medication was chosen based on institution specific protocol. (ACOG Safe Motherhood Initiative)

Oral nifedipine protocol

Nifedipine 10mg oral was given and the systolic and diastolic blood pressures were recorded 20 minutes after the medication was given. If SBP was ≥ 160 mmHg or DBP was ≥ 110 mmHg,

nifedipine 20mg oral was given and the systolic and diastolic blood pressures were recorded 20 minutes after medication was given. If SBP is ≥ 160 mmHg or DBP is ≥ 110 mmHg, nifedipine 20mg oral was given and the systolic and diastolic blood pressures were recorded 20 minutes after medication was given. If SBP was ≥ 160 mmHg or DBP was ≥ 110 mmHg, then another medication was chosen based on institution specific protocol. (ACOG Safe Motherhood Initiative)

Statistical Analysis

In the following sample size calculation, our primary aim is to detect an interaction effect between race and hypertensive treatment on time to reach goal blood pressure. We assume that the race distribution would be 20% for African Americans and 80% for Caucasians or Asians entering the clinic during the trial enrollment period. Randomization will be stratified by race at a 1:1 ratio to Nifedipine or Labetalol.

We assume the minimally clinical difference for African American patients on Labetalol is expected to take 30 minutes longer compared to patients on Nifedipine to reach their goal blood pressure. For Caucasian or Asian patients, those on Labetalol are expected to take 20 minutes longer compared to those on Nifedipine to reach their goal blood pressure. We expect residuals to be normally distributed with a mean of 0 and standard error of 8. We assume that time to goal blood pressure is normally distributed and power to detect an interaction by a linear regression is at least 85% with an alpha of 0.05.

Based on the above, we used a simulation approach to estimate that we would need a total of 146 patients to provide at least 85% power to detect an interaction effect between race and hypertensive treatment.

Power	Assumed Effect Size for African Americans	Assumed Effect Size for Caucasians or Asians	Assume Proportion of African Americans	Minimal Number of African Americans	Minimal Number of Caucasians or Asians	Total N
0.85	30 min	20 min	40%	40	58	98
0.90	30 min	20 min	40%	46	68	114

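### Blood pressure is read every 10 minutes on labetalol but every 20 on nifedipine, with no reading described after the third dose, so time to goal would be measured differently by arm

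*Combined protocol and SAP*

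**What the plan says.** The IV Labetalol protocol section states "Labetalol 20mg IV was given over 2 minutes and the systolic and diastolic blood pressures were recorded 10 minutes after the medication was given". The same interval follows the second dose and the third: "labetalol 80mg IV was given over 2 minutes and the systolic and diastolic blood pressures were recorded 10 minutes after the medication was given". The Oral nifedipine protocol section states "Nifedipine 10mg oral was given and the systolic and diastolic blood pressures were recorded 20 minutes after the medication was given", and repeats the 20-minute interval for doses two and three. In both arms, a patient still above threshold after dose three leaves the schedule: "then another medication was chosen based on institution specific protocol". No reading time is given from there on. The only general statement, in the Protocol section, is "The systolic blood pressure and diastolic blood pressure was recorded before and after administration of each medication", which sets no clock.

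The Statistical Analysis section says "our primary aim is to detect an interaction effect between race and hypertensive treatment on time to reach goal blood pressure". It plans on a linear regression with normally distributed times and a residual spread of 8. It also says that "African American patients on Labetalol is expected to take 30 minutes longer compared to patients on Nifedipine", with 20 minutes as the corresponding figure for Caucasian or Asian patients. The documents do not say how time to goal is derived from the readings, whether other readings are taken, or what mean time is expected in either arm.

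**The concern.** The only timed post-dose readings come twice as often in one arm as in the other. If the endpoint is built from them, a patient who is truly at goal at 8 minutes is recorded as 20 on nifedipine and as 10-12 on labetalol. Two nifedipine patients who reach goal at different moments within one 20-minute interval get the same time. The labetalol-minus-nifedipine difference within each race would then mix drug effect with reading schedule. The interaction is built from those two differences.

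The schedule also ends early in the arm assumed to be slower. The last labetalol reading is at about 30-36 minutes, yet labetalol is expected to take 20 or 30 minutes longer than nifedipine. Many labetalol patients would therefore reach goal after the last described reading, and their recorded time depends on an unwritten rule.

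**Working it through.** **The plan's own figure.** Inputs from Statistical Analysis: interaction 30 - 20 = 10 minutes, SD 8 (called a standard error there), 20% African American, 1:1 within race, alpha 0.05 (taken as two-sided), power 85%.

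N = (1.960 + 1.036)² × 8² × (4/0.2 + 4/0.8) / 10² = 8.98 × 64 × 25 / 100 = 143.7, against the stated 146. Noncentral t power at 146 is 0.851. The sample size reproduces if times are observed exactly.

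**Reading times.** If each further dose follows at once, labetalol readings fall at 10/20/30 minutes, or 12/24/36 counting the 2-minute injections. Nifedipine readings fall at 20/40/60.

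**Rough size of the shift.** Rounding up to the next reading adds about half an interval: 20/2 - 10/2 = 5 minutes, or 20/2 - 12/2 = 4 minutes, longer on nifedipine.

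**Simulation.** Assumptions: true times are normal with SD 8; nifedipine means are 10, 15, 20, 25 or 30 minutes (not given in the documents); labetalol means are 20 and 30 minutes longer; goal is seen only at a reading. With identical true times in both arms, nifedipine is recorded 4.0-4.8 minutes longer (12-minute labetalol grid) or 5.0-6.0 (10-minute grid). With the planned effects:

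| Labetalol after dose three | Nifedipine mean | Recorded differences (true 20 / 30) | Recorded interaction (true 10) |
|---|---|---|---|
| Read every 10-12 min until goal | 15-30 | 14.7-16.0 / 24.7-26.0 | 10.0 |
| Same | 10 | 12.9-13.9 / 22.9-23.9 | 10.0 |
| Read every 20 min until goal | 15-30 | 18.7-20.0 / 29.4-30.3 | 9.7-11.0 |
| Same | 10 | 15.6-16.9 / about 27.9 | 11.0-12.3 |
| Scored at the third reading | 10-30 | from -10.0 to 13.6 | 2.6 or less |

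The table places the race effect on labetalol times. If it acts on nifedipine times, with labetalol readings continued every 10-12 minutes, the interaction is recorded as 8.0 for means of 10 versus 20, because the 20-minute floor binds in one race only. It is 9.5-10.0 for slower means.

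**Why the last row is so low.** The share of labetalol times beyond 36 minutes, for nifedipine mean m, is:
- Caucasian or Asian: 1 - Φ((36 - m - 20)/8), which is 23% at m = 10, 69% at m = 20 and 96% at m = 30.
- African American: 1 - Φ((36 - m - 30)/8), which is 69%, 96% and 99.9%.

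Scoring at 36 minutes gives interactions of 2.6 at m = 10, 1.0 at 15, and 0.3 or less at 20-30.

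**Power at N=146** (29 African American, 117 others; four-cell regression):
- Exact times: 85%.
- Described intervals continued every 10-12 minutes on labetalol: about 71-78% at means 15-30. At mean 10 it is 89%, because most nifedipine times collapse onto 20 and lose their spread.
- Common 10-minute clock until goal: about 80-83% at means 15-30.

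These figures hold only if SD 8 describes true times; the plan does not say whether it refers to true or recorded times.

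**The case against.** The strongest reply is that no single bias can be read off the plan. A reader might infer that nifedipine times are simply recorded 4-6 minutes too long. The documents do not support that as a fixed figure: it needs labetalol readings every 10-12 minutes after dose three, where none are described and where the plan's own effects place many or most labetalol patients. With 20-minute readings there, an assumption no less documented, the shift at means 15-30 is about 0-1.3 minutes. This stands, so the size must be given by scenario.

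Second, the primary aim is the interaction, and the within-race differences appear only as planning assumptions. A common shift cancels in the interaction. This stands when labetalol readings continue every 10-12 minutes and race acts on labetalol times. It does not stand as a general reassurance: the interaction collapses if patients are scored at the third reading, and coarse readings cost power even where the mean shift cancels.

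Third, the 10- and 20-minute checks are the dose-decision points of the two regimens, so a longer wait is partly a feature of the strategies compared. That is fair for treatment decisions. It does not require the endpoint to be measured only at those points.

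Finally, the methods are largely in the past tense, so adding readings may no longer be possible, and extra cuff readings may exist without being described. Either would change the remedy, and extra readings would shrink the problem. Neither removes the need to say how time to goal is obtained.

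**Conclusion.** The concern holds in conditional form. As described, the readings give the primary endpoint an arm-dependent floor (about 10-12 versus 20 minutes), resolution and last observed time (about 30-36 versus 60 minutes). The consequence runs from almost none to loss of most of the interaction, depending on what happens after dose three, on the nifedipine mean, and on whether SD 8 describes true times.

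A reader might also infer that the sample size is wrong or that the primary interaction is necessarily biased. Neither follows: 146 reproduces under the stated assumptions, and the interaction estimate stays near 10 in some plausible scenarios. What the documents do show is that the assumed 20- and 30-minute differences sit badly with a labetalol schedule ending at about 30-36 minutes, and these must be reconciled. This is an improvement worth considering, held with medium confidence.

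**What to change.** For endpoint ascertainment only, record pressure on the same clock in both arms, for example every 10 minutes from the first dose, until goal is reached and including after a change of medication. Define time to goal from those readings. Leave the dosing-decision points as written. State how patients who move to another medication are counted, and reconcile the assumed differences with the last scheduled labetalol reading.

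Under the assumptions above, this clock with the planned regression records the true 20 and 30 minutes as 18.9-20.0 and 28.9-30.0. The cost is a few extra readings, since pressure is already "taken in the right arm with an automated blood pressure cuff while the patient was resting in bed", plus one endpoint definition. Power is about 80-83% at means 15-30, so the stated 85% should be rechecked.

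If follow-up must stop at a fixed time, right-censor patients not at goal. With a 60-minute stop, scoring them at 60 gives interactions of 9.9, 9.7, 8.9, 7.4 and 5.0 across the five nifedipine means; right-censoring gives 9.9-10.1 with 79-81% power. This replaces the planned regression.

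If readings cannot be added, an interval-censored analysis of the existing ones is a fallback only. Its power is 62% at mean 10 and 72-74% at means 15-30 if the described intervals continue until goal. If readings stop at the third dose (labetalol 12/24/36), it is 61%, 65%, 56%, 26% and 2% across the five means, which is not adequate.

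### Do the scheduled blood pressure readings rule out the 30- and 20-minute effects behind the sample size of 146?

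*Combined protocol and SAP*

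**What the plan says.** The Statistical Analysis section opens by stating that "our primary aim is to detect an interaction effect between race and hypertensive treatment on time to reach goal blood pressure". For the sample size it assumes that "African American patients on Labetalol is expected to take 30 minutes longer compared to patients on Nifedipine to reach their goal blood pressure", and that among Caucasian or Asian patients "those on Labetalol are expected to take 20 minutes longer compared to those on Nifedipine to reach their goal blood pressure". On variability it says "We expect residuals to be normally distributed with a mean of 0 and standard error of 8". It concludes that "we would need a total of 146 patients to provide at least 85% power to detect an interaction effect between race and hypertensive treatment".

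The reading times come from the two medication protocols. For labetalol, "Labetalol 20mg IV was given over 2 minutes and the systolic and diastolic blood pressures were recorded 10 minutes after the medication was given"; the third and last step reads "labetalol 80mg IV was given over 2 minutes and the systolic and diastolic blood pressures were recorded 10 minutes after the medication was given". For nifedipine, "Nifedipine 10mg oral was given and the systolic and diastolic blood pressures were recorded 20 minutes after the medication was given", and the two further doses are also read at 20 minutes. In both arms a further dose follows if systolic pressure is at least 160 or diastolic at least 110 mmHg. After a third failure the patient moves to a different drug chosen by local practice. The plan does not define goal, does not say when the clock starts or stops, and does not say how time is counted after that move.

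**The concern.** The only blood pressure threshold in the plan is the re-dosing trigger, so it is natural to take goal as below 160/110. On that reading, and counting only the randomised drug, labetalol is checked sooner and more often than nifedipine and its three-dose course ends earlier. A plan that expects labetalol to be 20 or 30 minutes slower then seems to contradict its own schedule. Since those two effects and the SD of 8 are the stated basis for 85% power on the primary aim, the power claim would have no support for the endpoint as recorded. Two analysts could also give different times to the same patient, for example one who switches drug after the third dose.

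**Working it through.** **Inputs.** From Statistical Analysis: effects of 30 and 20 minutes, residual SD 8 (the plan writes standard error; only the SD reading reproduces its numbers), alpha 0.05 taken as two-sided, 20% African American, 1:1 allocation within race. From the medication protocols: each labetalol dose is a 2-minute push plus a 10-minute wait, each nifedipine dose a 20-minute wait, three doses per drug.

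**1. The plan's own figure.** The interaction is 30 − 20 = 10 minutes. By the normal approximation,

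N = 4 × 8² × (1/0.2 + 1/0.8) × ((1.960 + 1.036)/10)² = 1600 × 0.0898 ≈ 144.

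The noncentral t gives exactly 146, with power 0.851. With whole-patient cells of 15, 14, 59 and 58, SE = 8 × √(1/15 + 1/14 + 1/59 + 1/58) = 3.32, and power is 0.849. The two 40% rows of the table reproduce from the same inputs: power is 0.853 at 98 patients and 0.901 at 114. Only the 10-minute contrast and the SD enter. Any other pair of effects 10 minutes apart gives the same N.

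**2. The cap on the narrow reading.** With no delay between a reading and the next dose, labetalol readings fall at 12, 24 and 36 minutes and nifedipine readings at 20, 40 and 60. The largest possible excess for labetalol is 36 − 20 = 16 minutes, or 30 − 20 = 10 if the push is not counted. Effects of 30 and 20 would need labetalol means of at least 50 and 40 minutes, both beyond 36. On this reading they cannot be recorded.

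**3. Does the 10-minute interaction survive the cap?** Yes: differences of 16 and 6, or 12 and 2, are inside it. If both arms are also to have SD 8 on these reading times, the largest mean difference is about 32.95 − 21.67 = 11.3 minutes, so a pair such as 11 and 1 is not excluded. If labetalol is not faster in either group, a difference of at least 10 in African American patients needs a labetalol mean of at least 30. Then 36 − 12p₂ − 24p₁ ≥ 30, where p₁ and p₂ are the shares reaching goal at the first and second readings, so at least half must reach goal only at the third. That is demanding but possible, and it loosens if labetalol may be faster in Caucasian or Asian patients.

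**4. Are 30 and 20 possible if time on the further drug counts?** Take all nifedipine patients at goal at 20 minutes, labetalol successes at 36 and labetalol failures at goal at 56 on the next drug. A failure share f gives a labetalol mean of 56f + 36(1 − f). Setting this to 50 gives f = 0.70; setting it to 40 gives f = 0.20. Both effects then occur as written.

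**5. What this does to power.** These are simulations of 146 patients on invented response shares, always with a 10-minute interaction.

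| Case | SD | Power |
|---|---|---|
| Within the cap, effects 12 and 2 | 7.7 | 92% |
| Within the cap, 11 and 1 | 9.2 | 78% |
| Within the cap, 10 and 0 | 10.4 | 66% |
| Further drug counts, 30 and 20, successes at 36, failures at 56 | 5.9 | 96% |
| Same, failures at 66 | 8.0 | 79% |
| Same, failures at 76 | 9.7 | 64% |

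With earlier labetalol successes and later failures, power falls as low as 20%. The results lie on both sides of 85%, and no response share comes from the documents.

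**The case for a change.** The strongest case for a change is that the plan supports its 10-minute interaction only as 30 minus 20. If neither level can be recorded, the 10 loses its stated support, even though the arithmetic from 10 to 146 is sound. The ways out (time on a further drug, a different goal, delays, unscheduled readings) are nowhere written down. Nor would an interaction of 10 with a pooled SD of 8 guarantee 85% on recorded times. In the case with failures at 66 minutes, the labetalol variances are 30² × 0.467 × 0.533 = 224 and 30² × 0.133 × 0.867 = 104, against 0 on nifedipine. With such unequal cells the pooled test has 79% power and rejects the true 10-minute interaction about 12% of the time.

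Part of this stands. Goal, clock and switching are undefined, and the stated power cannot be checked on recorded times. The claimed impossibility does not stand, because it needs two conditions that the plan never sets. The trigger is used only to decide the next step and is never called goal. Counting only the randomised drug is the weaker condition: randomisation fixes which drug comes first, doses are counted for each drug, a further drug is foreseen, and nothing stops the clock at the switch. The protocol also follows an external dosing guideline that may set a goal; that cannot be checked from the documents.

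**Conclusion.** No change follows. The 16-minute cap (10 without the push) is correct arithmetic, but it is conditional on goal meaning below 160/110, on counting only the randomised drug, and on protocol timing being kept. If time on the further drug counts, which the plan's wording leaves open, 30 and 20 minutes are attainable. On either reading the sample size stands on its own terms: a 10-minute interaction with SD 8, tested two-sided at 0.05, gives 85% power at 146, and 10 minutes fits inside the cap.

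What is left is missing detail. The plan records pressure before and after each dose and counts the doses, so analysts have the material to fix goal, clock and the handling of switchers when they derive the endpoint. The power illustrations point in no single direction and rest on assumed response shares. They show that power depends on unstated inputs; they do not show that 146 is too few, and they yield no better number to put in its place.

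### The 85% power for 146 patients treats time to goal as continuous and normal, with no allowance for the protocol's 10- and 20-minute readings or for where its labetalol schedule ends

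*Combined protocol and SAP*

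**What the plan says.** The Statistical Analysis section makes the race-by-treatment interaction on time to goal blood pressure the primary aim.

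- **Distribution:** "We assume that time to goal blood pressure is normally distributed" and "We expect residuals to be normally distributed with a mean of 0 and standard error of 8".
- **Effects:** "African American patients on Labetalol is expected to take 30 minutes longer compared to patients on Nifedipine", and "For Caucasian or Asian patients, those on Labetalol are expected to take 20 minutes longer compared to those on Nifedipine".
- **Result:** "power to detect an interaction by a linear regression is at least 85% with an alpha of 0.05", from which "we would need a total of 146 patients to provide at least 85% power to detect an interaction effect". A table adds totals of 98 (85% power) and 114 (90% power) for a 40% African American share.

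The dosing sections set the readings. In the IV Labetalol protocol, "blood pressures were recorded 10 minutes after the medication was given", with each dose injected over 2 minutes. In the Oral nifedipine protocol, "blood pressures were recorded 20 minutes after the medication was given". Each schedule has three doses. If pressure is still high at the third reading, the choice of another drug passes to the institution's own protocol.

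The documents do not say how time to goal is derived from these readings, what happens to it after the third reading, what mean time is expected on nifedipine, or whether the 8 refers to true or recorded times.

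**The concern.** The sample-size model and the measurement schedule describe different outcomes. On the scheduled readings, time to goal takes a few values, spaced 20 minutes apart in one arm and 10 or 12 in the other. A 20-minute step is 2.5 times the assumed SD and twice the 10-minute interaction being tested. Such a variable is not the continuous normal one behind the 85%.

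The end of the schedule raises a second difficulty. The assumed differences put labetalol 20 and 30 minutes behind nifedipine, yet the last scheduled labetalol reading falls soon after the first nifedipine reading.

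The interaction is the stated primary aim. If its power is materially below the stated figure, a null result would be read as stronger evidence against an ethnic difference in response than it is.

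**Working it through.** **Inputs.** From Statistical Analysis: effects of 30 and 20 minutes, residual spread 8, alpha 0.05 (taken as two-sided), N = 146, 20% African American, 1:1 allocation within race. From the dosing sections: the reading intervals and three doses per drug. The stated standard error of 8 is read as the per-patient residual SD, because only that reading reproduces N. The nifedipine mean is not given, so it is varied.

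**1. The plan's own figure.** The interaction is 30 − 20 = 10 minutes. Twenty percent of 146 is about 29, leaving 117, so the cells are 14, 15, 58 and 59.

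SE = 8 × √(1/14 + 1/15 + 1/58 + 1/59) = 8 × √0.1723 = 3.32, and 10/3.32 = 3.01.

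Power is Φ(3.01 − 1.96) = 85.3%; the noncentral t with 142 df gives 84.9%. The table rows also reproduce (noncentral t): 40/58 gives 85.3% and 46/68 gives 90.1%. The stated inputs therefore yield the stated figures, with no rounding of times.

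**2. Added variance if SD 8 describes unrounded times.** Moving a time up to the next reading at spacing g adds roughly g²/12.

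- Nifedipine: 64 + 400/12 = 97.3.
- Labetalol: 64 + 100/12 = 72.3.
- Sum: about 169.7, against 64 + 64 = 128.

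The SE grows by √(169.7/128) = 1.15, to 3.82, and power falls to about 74% (73% with a 12-minute labetalol cycle).

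**3. Simulation on the readings.** Normal times with SD 8 are moved up to the next reading, with nothing recorded before the first. The nifedipine mean is the same in both race groups, and there are 8,000 runs per setting (Monte Carlo error about ±1 point). The *continued* columns keep the same spacing after the third dose. The *capped* columns stop labetalol at its third reading (30 or 36 minutes) and nifedipine at 60.

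| Nifedipine mean (min) | Continued, 10-min labetalol | Continued, 12-min | Capped at 30 | Capped at 36 |
|---|---|---|---|---|
| 5 | 95.8% | 94.8% | 34.3% | 68.1% |
| 10 | 89.4% | 88.6% | 4.8% | 17.2% |
| 12 | 85.6% | 84.6% | 5.3% | 9.0% |
| 14 | 81.2% | 79.6% | 5.2% | 5.9% |
| 15 | 79.7% | 78.4% | 5.4% | 5.9% |
| 20 | 72.1% | 70.6% | 5.7% | 5.8% |
| 30 | 77.5% | 76.4% | 5.2% | 6.1% |
| 40 | 70.1% | 69.0% | 5.8% | 5.9% |
| 50 | 76.2% | 76.5% | 4.9% | 4.7% |

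In the continued columns the estimated interaction stays at about 10 minutes, so the loss is one of variance. At low nifedipine means the first reading at 20 minutes compresses the nifedipine times, which is why power rises there. In the capped columns the estimated interaction shrinks to about 1 minute or less from a mean of 15 upward.

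With continued readings and nifedipine means of 20-40, the 98-patient row gives 70-80% and the 114-patient row 77-85%; these ranges include the case of labetalol times recorded exactly. If the nifedipine mean differs by 5 or 10 minutes between race groups, power at 146 ranged from 23% to 78% in the cases tried.

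**4. What the schedule allows.** The first nifedipine reading is at 20 minutes. The third labetalol reading is at 3 × 10 = 30 minutes, or 3 × 12 = 36 with the injections. The largest labetalol excess on scheduled readings is therefore 30 − 20 = 10 or 36 − 20 = 16 minutes, against the assumed 20 and 30. This does not depend on what the 8 describes.

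**The case against.** The arithmetic is not wrong: the stated inputs give the stated power. The strongest defence is that residuals in a linear regression belong to the variable analysed. The 8 is then the SD of recorded times, and rounding adds nothing. That stands as far as it goes. But on a 20/40 grid an SD of 8 needs 20 × √(p(1 − p)) = 8, so p(1 − p) = 0.16 and 80% of nifedipine patients at one step. The plan says nothing of the kind, and such an outcome is not normal. Nor does this reading remove the conflict in step 4.

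A reader might infer that 146 patients simply deliver 70-79% power. The documents do not support that as an unconditional figure, for three reasons.

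- It needs SD 8 to describe unrounded times, which the text does not state.
- It needs a nifedipine mean of about 15 minutes or more. At about 12 or less, power is kept or exceeded. That region fits poorly with the plan's normality assumption, since about 7% of times would be negative at a mean of 12 and about 11% at 10, but the documents do not exclude it.
- It needs labetalol readings beyond the third dose, which the protocol does not schedule. At a nifedipine mean of 20, 89% of Caucasian or Asian and 99% of African American labetalol times exceed 30 minutes (69% and 96% exceed 36). Nearly all the simulated labetalol data rest on that assumption.

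A reader might also infer that no other readings are possible. The protocol lists scheduled readings and does not rule out others.

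**Conclusion.** The concern holds in conditional form. The 85% depends on a continuous normal outcome that the scheduled readings cannot yield, and the calculation makes no allowance for the difference.

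- **SD 8 on unrounded times, the same nifedipine mean of about 15 minutes or more in both race groups, readings continued at the same spacing:** about 70-80% power at 146, so a true 10-minute interaction is missed 20-30% of the time rather than 15%.
- **The same, with nifedipine means of about 12 minutes or less:** about 85% or more.
- **SD 8 on recorded times:** no loss from rounding, but the assumed 20- and 30-minute differences exceed the 10-16 minutes that the scheduled readings allow.
- **Labetalol capped at its third reading (underlying SD 8):** about 5-6% for nifedipine means of 15 minutes or more.

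The capped result should not be taken as the trial's actual power either, because the documents do not say that times stop at the third reading. No single power figure follows from the plan as written. That is the reason to correct it, and it bears on how a null result for the primary aim would be read.

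**What to change.** In Statistical Analysis:

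1. State how time to goal is recorded, including after the third dose and whether unscheduled readings count.
2. State whether SD 8 refers to true or recorded times.
3. Reconcile the assumed 20- and 30-minute differences with the reading schedule in the two dosing sections.
4. Re-run the existing simulation with each time placed on that schedule, over a stated range of nifedipine means, including means that differ between race groups.
5. Replace the claim of at least 85% for 146, and the powers in the 98 and 114 rows, with the resulting range and its assumptions.

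The cost is a few lines of simulation, a short definition, and a probably less favourable power figure. No change in enrolment or clinical management is proposed.

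### The primary interaction regression lists no covariate, although pressure before the first randomised dose is already recorded and could be pre-specified for a possible gain in precision

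*Combined protocol and SAP*

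**What the plan says.** The aim is stated at the start of Statistical Analysis: "our primary aim is to detect an interaction effect between race and hypertensive treatment on time to reach goal blood pressure". The only model named is in that section's second paragraph, as part of the sample size argument: "power to detect an interaction by a linear regression". There is no model equation and no term beyond race and treatment. Baseline pressure is neither included nor excluded. On the error term the section says: "We expect residuals to be normally distributed with a mean of 0 and standard error of 8". It does not say whether that spread is before or after any adjustment. Allocation is balanced within race: "Randomization will be stratified by race at a 1:1 ratio to Nifedipine or Labetalol".

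The Protocol section shows that the candidate covariate is collected: "The systolic blood pressure and diastolic blood pressure was recorded before and after administration of each medication". It also fixes which reading is a true baseline: "Patients were randomized to first receive IV labetalol or oral nifedipine". Only the reading before that first dose precedes treatment.

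**The concern.** The primary aim is an interaction, which is estimated much less precisely than a main effect. Here it rests on about 29 African American patients (20% of 146), and the planned 95% half-width is about 6.6 minutes against a 10-minute target. Planned power is almost exactly 85%, with no margin.

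Both dosing schemes continue until pressure falls below 160/110 mmHg. It is therefore plausible that a patient who starts further above that limit takes longer to reach goal. That is an inference; the documents give no figure for it. If it is true, part of the outcome variation could be removed with data already in hand. A second stake does not depend on the gain: while the model terms are unlisted, the choice to adjust or not can be made after the results are seen.

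**Working it through.** **Inputs (all from Statistical Analysis).** Effects are 30 and 20 minutes, so the interaction is 30 − 20 = 10 minutes. The residual spread of 8 is read as an SD. Alpha is 0.05, taken as two-sided because that reproduces the stated total. Allocation is 1:1 within race, with 20% of 146 African American, about 29 against 117.

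**1. The plan's own figure, without covariates.**
- SE = 8 × √(4/29 + 4/117) = 8 × √(0.1379 + 0.0342) = 8 × 0.4149 = 3.32 minutes.
- Residual df = 146 − 4 = 142; critical t = 1.977; half-width = 1.977 × 3.319 = 6.56 minutes.
- Noncentral-t power for 10/3.319: 84.9%.
- At an exact 20% split (29.2/116.8), power is 85.1%, and 146 is the smallest total that reaches 85%.
- The table rows also reproduce: 85.3% at 40/58 and 90.1% at 46/68. The table's 40% share against the text's 20% is a separate matter and does not affect this point.

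**2. Adding two baseline covariates.** Let R² be the share of within-cell variance in time to goal (cells are race by treatment) that the two first pre-dose pressures explain. It is an assumption throughout.
- Residual SD becomes 8 × √(1 − R²).
- Residual df = 142 − 2 = 140; critical t = 1.977.
- Chance imbalance in two covariates inflates the SE on average by √(141/139) = 1.0072.
- SE = 3.319 × √(1 − R²) × 1.0072.

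| Assumed R² | SE (min) | 95% half-width (min) | Power at 29/117 |
|---|---|---|---|
| Unadjusted | 3.32 | 6.56 | 84.9% |
| 0% | 3.34 | 6.61 | 84.4% |
| 1% | 3.33 | 6.58 | 84.8% |
| 4% | 3.28 | 6.48 | 85.8% |
| 10% | 3.17 | 6.27 | 87.9% |
| 20% | 2.99 | 5.91 | 91.3% |
| 30% | 2.80 | 5.53 | 94.4% |

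**3. Break-even.** The adjusted SE equals the unadjusted SE when (1 − R²) × 141/139 = 1, so R² = 1 − 139/141 = 1.4%. Below that, adjustment costs a little precision. The worst case is R² = 0, where power falls by 84.9 − 84.4 = 0.5 points.

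**4. Simulation check.** With 40,000 trials per scenario (cells 15/14/59/58, the two pressures correlated 0.5), adjusted power was 84.3, 84.8, 85.8, 88.0, 91.2 and 94.3% at R² of 0, 1, 4, 10, 20 and 30%, in line with the table. With a baseline slope twice as steep on nifedipine as on labetalol, the common-slope model still gave 87.4, 90.7 and 93.6% at R² of 10, 20 and 30%, with type I error of 4.9 to 5.2%.

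**5. If the 8 is already an adjusted SD.** Stated power does not change. The unadjusted SD would then be 8/√(1 − R²), larger than 8, and the covariates would be needed to reach the planned power.

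**The case against.** The strongest reply is that nothing here is wrong. A linear regression with race, treatment and their interaction is a legitimate primary model, no statement in the documents is contradicted, and the sample size reproduces. That stands, and it caps the point at an optional improvement.

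The gain also has no anchor in the documents. Every R², the 0.5 correlation and the 2:1 slope ratio are assumptions, and the resulting change in power runs from −0.5 to +9.5 points. That stands too. A spread described as belonging to residuals can fairly be read as what is left after whatever model is fitted, in which case the stated power gains nothing.

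The outcome model is a further doubt. The labetalol scheme says "labetalol 40mg IV was given over 2 minutes and the systolic and diastolic blood pressures were recorded 10 minutes after the medication was given", while the nifedipine scheme says "Nifedipine 10mg oral was given and the systolic and diastolic blood pressures were recorded 20 minutes after the medication was given". If time to goal is taken from these scheduled readings, the outcome is coarse and differs in grain by arm. The last scheduled labetalol reading falls at about 3 × (2 + 10) = 36 minutes. The earliest nifedipine value of 20 minutes plus the assumed 20 to 30 would put labetalol at 40 to 50. Definition of the outcome and handling of patients who move to another drug is a separate and prior question. It makes the decimals above approximate, but it does not remove the case for listing the model terms.

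A reader might infer more: that the unadjusted interaction is biased, that the trial is underpowered, or that adjustment is bound to narrow the interval. The documents support none of these. Randomisation within race protects the unadjusted estimate, the 84.9% against 85.1% is only rounding of the split, and below an R² of about 1.4% the interval widens slightly.

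**Conclusion.** The point holds as a low-cost improvement to consider. The plan's unadjusted analysis is valid, and 146 patients give about 85% power on its own assumptions. What is missed is a possible gain in precision from a value already recorded, and a commitment to the model terms before results are known.

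The gain is hypothetical: about 3 points of power at an assumed R² of 10% (84.9% to 87.9%), about 6 at 20%, none at about 1.4%, and a loss of about 0.5 at zero. This rests on the 8 being an unadjusted SD, on a continuous normal outcome, and on the 29/117 split. Confidence in the size is moderate at best, since the documents say nothing about how starting pressure relates to time to goal.

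**What to change.** Before outcome data are examined, write the primary model out: race, treatment, race-by-treatment, and continuous systolic and diastolic pressure taken before the first randomised dose, both as main effects. State that readings before later doses are not used as covariates, because they follow treatment. Report the unadjusted interaction alongside. State whether the 8 is a residual SD before or after adjustment. A baseline-by-treatment term belongs at most in an exploratory analysis, because it changes the question to the race difference at equal starting pressure.

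The cost is a few lines of text, 2 of 142 residual degrees of freedom, and at worst about 0.5 points of power. No new data are needed and the sample size of 146 need not change. The Protocol section is written in the past tense, so if outcomes have already been examined, the adjusted model should be labelled post hoc.
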